
Tear film SARS-nCoV-2 detection in symptomatic and pauci-symptomatic patients.

This research project intends to provide a more thorough understanding of the presence of this new virus in the tear film of SARS-nCoV-2 positive patients. Furthermore, it could provide insight in the timing of the contagiousness of tears and highlights correlations with other signs and symptoms.

[figure not shown]

Figure 1: study design.

2. Trial objectives and design

Primary outcome measures

- 1) The presence of SARS-nCoV-2 in the tear film of symptomatic and pauci-symptomatic SARS-nCoV-2 positive patients.
- 2) Correlations between SARS-nCoV-2 in the tear film and mild (like anosmia, ageusia, upper and lower respiratory tract infection) or severe symptoms (as pneumonia, need for hospitalization) of COVID-19.

Secondary outcome measures

- 1) The stage of disease when SARS-nCoV-2 becomes detectable in the tears.
- 2) Duration of shedding of SARS-nCoV-2 RNA in the tears.
- 3) Difference in RNA viral load (by means of quantitative result (Cycle threshold (Ct) of the SARS-nCoV-2 PCR) in tears of different patients at different moments in time in order to estimate potential difference in transmissibility of the virus by tears.
- 4) Assessment of evolution of quantitative result (Cycle threshold (Ct)) of the SARS-nCoV-2 PCR over time within conjunctival SARS-nCoV-2 PCR positive patients
- 5) Searching for a correlation between both quantitative and qualitative results of SARS-nCoV-2 PCR on the nasopharyngeal and conjunctival swab (both positive for SARS-nCoV-2; both negative for SARS-nCoV-2; discordant results, with either eye or nasopharynx positive and the corresponding sample negative for SARS-nCoV-2).

Tear film SARS-nCoV-2 detection in symptomatic and pauci-symptomatic patients.

- 6) Exploring the possibility of testing the tear film on SARS-nCoV-2 as a screening tool for early disease.
- 7) Exploring the replication of the SARS-nCoV-2 virus, by differentiating between death and alive SARS-nCoV-2 virus through sg RNA-testing and tissue culture.

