2.1 Preparation, organization and management of this exploratory study

Part 1: Serial sampling of symptomatic and confirmed positive patients

Patients will be informed about the study by a health care worker at a non-ICU unit (“rampen unit”) of the University Hospitals Leuven, Belgium.

In case a candidate is interested in participating and tested positive for SARS-nCoV-2 on his/her nasopharyngeal swab, he/she will be informed about the study goals by the same health care worker. The volunteer will receive an information letter and a copy of the informed consent to take home.

Study procedure

After signing the informed consent, each patient will be asked to fill in a questionnaire (cfr. *Addendum A*).

The simplicity of performing a conjunctival swab makes it possible **to implement in the daily routine** of health care workers, **avoiding additional waste of personal protective equipment.**

Conjunctival sampling will be performed on both eyes after the application of a drop of topical anesthesia (Minims® Oxybuprocaine Hydrochloride 0.4%, Bausch and Lomb, Aubenas, Frankrijk). A timed 5 minutes will be in between application of the drop and the sampling. The sampling will be performed by a trained nurse and/or medical student and/or resident after proper training of correct sampling (cfr *Addendum B*).

Each eye will be sampled with a single, sterile, nylon, flocked swab (FLOQSwabs®; Copan, Brescia, Italy). This FLOQSwabs® is a **different** swab than the one used for routine nasopharynx SARS-nCoV-2 testing.

The sampling will be done from the nasal to temporal inferior conjunctival sac, the swab will be swirled in the opposite direction of the sampling itself.

The swabs will be placed in a tube with universal transport medium (UTM) and transferred to a -80°C freezer until further processing.

The conjunctival swab will be tested for SARS-nCoV-2 presence by making use of in-house reverse transcription real-time polymerase chain reaction (RT-PCR) designed for routine diagnostics targeting specific SARS-nCoV-2 genes in the clinical laboratory of the University Hospitals Leuven or at the REGA institute (laboratory of [name]).

Tear film SARS-nCoV-2 detection in symptomatic and pauci-symptomatic patients.

Serial sampling

Sampling will be repeated every 3 days to evaluate if PCR becomes positive during the course of disease and to monitor the duration of detectability of the virus in tears.

Part 2: Single sampling of pauci – symptomatic patients

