4.1 Summary of visits

Part 1: Serial sampling of symptomatic patients

Sampling will take place at the “rampen unit” of the University Hospitals Leuven, Belgium. Once the patient is admitted and tested positive for SARS-nCoV-2 on nasopharyngeal swab, conjunctival sampling will take place every three days until the day of discharge. The time window between a positive nasopharyngeal swab and the first conjunctival swab may be no more than 3 days.

Part 2: Single sampling of pauci-symptomatic patients

Sampling will take place at the emergency department of the University Hospitals Leuven, Belgium by the swab team. The sampling will not be repeated.

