7.2 Analysis

The statistical analyses will be performed using statistical software such as R-studio or SPSS. The Shapiro-Wilk test will be used for normality testing. Depending their distribution, continuous variables will be summarized as mean \pm standard deviation or median with interquartile range. Categorical variables will be summarized in absolute numbers and percentages. All statistical test will be significant if the P-value ≤ 0.05 .

Primary outcome measures

The presence or absence of the virus in the tears is the primary objective. A multivariate analysis will be used to interpret the questionnaire.

Secondary outcome measures

Tear film SARS-nCoV-2 detection in symptomatic and pauci-symptomatic patients.

For secondary outcome measures, we first have to indicate the different disease stages. We define them as early, intermediate and late stadium, respectively indicated by onset disease symptoms (cough, fever, fatigue, myalgia and lesser reported symptoms such as headache, diarrhea and abdominal pain, ageusia and anosmia, conjunctivitis), development of chest pains and dyspnea with need for hospitalization and eventually development of SARS and need for ICU administration (12). We also define a remission stage in which symptoms start to decline.

For investigation of the disease stage in which the SARS-nCoV-2 becomes detectable in the tears we aim to use an ANOVA analysis.

8. Quality assurance

To assure maximal quality and reproducibility, the trial protocol will be followed rigorously.

9. Direct access to source data and documents

Only data gathered in the context of the trial will be used.

10. Ethics and regulatory approvals

The trial will be conducted in compliance with the principles of the Declaration of Helsinki (2008), the principles of Good Clinical Practice and in accordance with all applicable regulatory requirements. This protocol and related documents will be submitted for review to Ethics Committee of the University Hospitals Leuven.

The Study will be conducted only on the basis of prior informed consent by the Subjects to participate in the Study. We shall obtain a signed informed consent form (ICF) for all patients prior to their enrollment and participation in the Study in compliance with all applicable laws, regulations and the approval of the (local) Ethics Committee, if required. We shall retain such ICFs in accordance with the requirements of all applicable regulatory agencies and laws.

11. Data Handling

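### Section 7.2 names only an ANOVA for the stage at which virus becomes detectable in tears; run per swab it would have wrong error rates in both directions, and it would not show when detection starts

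*Combined protocol and SAP*

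**What the plan says.** Section 2 lists as secondary outcome 1: "The stage of disease when SARS-nCoV-2 becomes detectable in the tears". The only analysis given for it is in section 7.2: "For investigation of the disease stage in which the SARS-nCoV-2 becomes detectable in the tears we aim to use an ANOVA analysis". Section 7.2 also sets a threshold of P ≤ 0.05 for every test. It describes early, intermediate, late and remission stages in general clinical terms.

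The data come from two different schedules. In Part 1 (section 2.1), "Sampling will be repeated every 3 days to evaluate if PCR becomes positive during the course of disease". Section 4.1 starts that sampling "Once the patient is admitted and tested positive for SARS-nCoV-2 on nasopharyngeal swab" and continues it until discharge. Part 2 is sampled once.

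On the eyes, section 2.1 says "Each eye will be sampled with a single, sterile, nylon, flocked swab", then "The swabs will be placed in a tube with universal transport medium (UTM", and then "The conjunctival swab will be tested for SARS-nCoV-2 presence". The move from two swabs to one tube to one tested swab does not show whether a visit gives one result or two. Addendum B describes a single brush broken off into its holder, which is closed at once. That points towards one tube per swab but does not say how results are reported.

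**The concern.** The ANOVA sentence leaves open four things that determine the answer: the response, the unit (eye, visit or patient), the treatment of repeated swabs from one patient, and the stage assigned to each swab. Two analysts could take the same data and reach different conclusions, both within the plan.

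The method also sits badly with the question. Serial swabs are taken to see when tears turn positive. An ANOVA of positivity across stages compares detection frequency between stages; it does not estimate when detection begins.

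The stage variable has problems of its own:

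- **Overlap with Part.** The intermediate stage in section 7.2 includes a need for hospitalisation, while Part 2 (section 3.1) admits only patients without that need. Early versus intermediate is therefore largely a comparison of Part 2 with Part 1. The overlap is not complete, because section 2.1 lets inpatients with another condition into Part 2.
- **Remission.** No source or rule for dated symptom decline is stated. The questionnaire is described once, after consent, and asks for onset dates.
- **ICU stage.** Follow-up is unclear. Sections 1 and 4.1 sample until the end of the stay, but section 4.1 places sampling on the unit where, in section 2.1, "Patients will be informed about the study by a health care worker at a non-ICU unit".

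**Working it through.** The plan gives no sample size, power or effect size for this outcome, so there is no figure of its own to reproduce.

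**Assumed inputs.** 50 to 192 patients per Part, true positivity 5% to 20%, within-patient correlation ρ of 0.2 to 0.5 (the same between eyes and between visits), 3 or 4 Part 1 visits, and no true difference. The upper size follows from section 7.1 if its margin is read as ±5 points and a rate of 50% is assumed: 1.96² × 0.25 / 0.05² = 384.1, rounded up to 385, or about 192 per Part if split equally.

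**Between Parts, one row per swab result.** With m₁ results per Part 1 patient, m₂ per Part 2 patient and equal numbers of patients, each Part's variance is inflated by D = 1 + (m − 1)ρ. The true variance of the difference, divided by the variance the ANOVA assumes, is

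R = (D₁/m₁ + D₂/m₂) / (1/m₁ + 1/m₂),

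and the actual type I error is approximately P(χ²₁ > 3.84/R).

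| Results per visit | Part 1 visits | ρ | D₁ | D₂ | R | Type I error |
|---|---|---|---|---|---|---|
| 1 | 3 | 0.2 | 1.4 | 1.0 | 1.10 | 6.2% |
| 1 | 4 | 0.5 | 2.5 | 1.0 | 1.30 | 8.6% |
| 2 | 3 | 0.2 | 2.0 | 1.2 | 1.40 | 9.8% |
| 2 | 4 | 0.5 | 4.5 | 1.5 | 2.10 | 17.6% |

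Beta-binomial simulation over 36 combinations of the inputs (4,000 runs each) agrees: 8.9% to 18.6% with two results per visit and 5.6% to 9.5% with one.

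**Earlier versus later visits of the same patients.** The patient effect now cancels, so R = 1 − ρ. For ρ = 0.2, P(χ²₁ > 3.84/0.8) = 2.8%. For ρ = 0.5, P(χ²₁ > 3.84/0.5) = 0.6%. The simulated range is 0.4% to 3.4%.

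**Power for that contrast.** Positivity falls from 10% to 5%, with 4 visits (two earlier, two later):

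| Patients | ρ | ANOVA | Patient-clustered GEE |
|---|---|---|---|
| 100 | 0.5 | 46% | 62% |
| 192 | 0.5 | 80% | 89% |
| 100 | 0.2 | 48% | 51% |
| 192 | 0.2 | 78% | 81% |

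A separate simulation with one result per visit and a paired patient-level test gave 46% versus 62% and 80% versus 88% at ρ = 0.5. The loss is material at high correlation and about 3 points at low correlation.

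**One result per patient.** Simulated type I error is 4.0% to 5.8%.

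**The case against.** Section 7.2 never says the ANOVA is per swab. It could mean a repeated-measures ANOVA, one result per patient, or a continuous response such as Ct or days since onset. This stands: every error rate above applies only to the per-swab reading, and the inputs are assumed. It does not remove the gap. Section 2 attaches Ct to other secondary outcomes, and no section supplies a repeated-measures model or a patient-level summary.

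A reader might infer that ANOVA fails because the result is binary. The check does not support that, since one result per patient gives nearly nominal type I error. The trouble is the clustering and the question asked.

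A reader might also infer that remission cannot be assigned at all, because section 9 restricts use to data gathered in the trial and the questionnaire has no resolution dates. That goes too far. Section 1 plans to use routine blood results in describing disease stage, so routine-care data are not clearly excluded, and recording symptom decline need not mean new data collection. Nor do the documents rule out ICU swabs, given sampling to the end of the stay. In both cases the supportable statement is that the source or rule is not given.

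Finally, this is a secondary outcome in a study that calls itself exploratory and a pilot, and no decision rule depends on it. That limits the weight.

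**Conclusion.** The point holds in conditional form. The plan names one method, ANOVA, for a repeated detected/not-detected outcome and states no response, unit or handling of within-patient correlation. Run per swab, it would reject too often between Parts (about 9% to 19% with two results per visit, about 6% to 10% with one) and too rarely within patients (about 0.4% to 3.4%), which is the comparison serial swabbing is meant to inform. These figures rest on the assumed sample sizes, positivity, correlation and visit numbers. They do not show that the trial will have such error rates.

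Two parts of the point need no assumed inputs. An ANOVA of positivity by stage would not estimate when virus first becomes detectable, and stage largely overlaps with Part without a rule for assigning it at each swab. Weight: minor to should-fix.

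**What to change.** Replace the ANOVA sentence in section 7.2 with the following.

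- **(a) Unit.** One result per patient-visit, positive if either eye is positive. State whether the eyes are pooled, since section 2.1 and Addendum B leave this unsettled.
- **(b) Model.** In patients with a positive nasopharyngeal PCR (not an entry requirement for Part 2), model patient-visit positivity on days since symptom onset. Use logistic regression clustered on patient (GEE or mixed), with Part as a covariate. Addendum A already collects the onset date. With fewer than about 30 tear-positive patients, report estimates with intervals only, or use a patient-level permutation test. In simulation, GEE type I error for the time slope reached 15.5% when about 7 to 30 patients were tear-positive, and was 5.3% to 6.0% with about 55 or more. The permutation test gave 3.5% to 5.6%.
- **(c) Stage.** Keep the stated outcome as a table of positivity by stage at each swab, under a written assignment rule, and note the overlap with Part. Leave out remission or ICU stage if no dated trial data support them.
- **(d) First detection.** Report time to first positive tear swab in Part 1 descriptively. Sampling starts only after admission and a positive nasopharyngeal test, so a positive first swab does not date the onset of detection and a negative one does not exclude earlier positivity. Discharge may also be informative.

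**Cost.** Rewording of section 7.2 and modest extra analysis, using swab results and onset dates already planned. Precision will be limited if positives are few, and Part as a covariate absorbs much of any early-versus-intermediate difference.

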Hebt u de afgelopen dagen een verstopte neus ervaren?	Ja	Nee/...../.....
Moest u sinds kort meer en/ of heviger hoesten ?	Ja	Nee/...../.....
Bent u de afgelopen dagen kort van adem geweest?	Ja	Nee/...../.....
Hebt u pijn op de borst ervaren de voorgaande dagen?	Ja	Nee/...../.....

Tear film SARS-nCoV-2 detection in symptomatic and pauci-symptomatic patients.

Hebt u de afgelopen dagen koorts gemeten (een temperatuur boven de 38,5°)?	Ja	Nee/...../.....
Hebt u de afgelopen dagen spierpijnen ervaren?	Ja	Nee/...../.....
Hebt u de afgelopen dagen hoofdpijn ervaren?	Ja	Nee/...../.....
Hebt u de afgelopen dagen last gehad van diarree ?	Ja	Nee/...../.....
Hebt u de afgelopen dagen last gehad van buikpijnklachten ?	Ja	Nee/...../.....

Addendum B: Explanation of the sampling

1. Bij het afnemen van het staal draai je de borstel in de tegengestelde richting van de beweging. Voor het linker oog is dat tegenwijzerzin, voor het rechter oog is dat wijzerzin (geheugensteuntje: wrijven weg van de neus, draaien naar de neus)
2. Plaats de borstel in het universeel transport medium (UTM)
3. Plaats het UTM met staal in de koelkast op -18°C
4. Binnen de 24 u moet het UTM met staal verplaatst worden naar -80°C

De steriele wisscher openen aan de kant van de steel, dus weg van de borstel (vermijd direct contact met de borstel!).

De steriele wisscher vasthouden aan de steel, zo ver mogelijk van de borstel om bijbesmetting van de handen te vermijden.

De steriele wisscher vasthouden aan de steel, zo ver mogelijk van de borstel om bijbesmetting van de handen te vermijden.

Naar boven kijken en met de wijsvinger het onderooglid naar beneden trekken.
De borstel mag enkel de binnenkant van het ooglid aanraken, niet de buitenkant.

De borstel zacht glijden aan binnenkant ooglid van de neuskant naar de oorkant.
Draai de borstel in de tegengestelde richting, cf punt 4.

De borstel mag enkel de binnenkant van het ooglid aanraken, niet de buitenkant.
Houd bovendien ook afstand van de borstel.

[name]®

Na staalname de borstel onmiddellijk overbrengen naar de houder. Probeer aanraking met de borstel te allen tijde te vermijden!

Enkele cm's boven het borsteltje is er een rode verkleuring. Door deze op de rand van de houder te leggen, kan de borstel losgekraakt worden van de steel. de

[figure not shown]

Sluit onmiddellijk de houder en bewaar deze in de diepvries bij -20°C gedurende maximaal 2 dagen, nadien te bewaren op -80°C.

Tear film SARS-nCoV-2 detection in symptomatic and pauci-symptomatic patients.

Nasofaryngeale afname procedure

1

(Relatieve) contra-indicaties:

- Ziekte van Rendu-Osler-Weber
- Ernstige thrombopenie ($< 15,10^9/l$)
- Recente neus cauterisatie en/of chirurgie

Consulteer de behandelende arts bij twijfel

[figure not shown]
1

Buig het hoofdlichtjes
naar achteren en breng de
Swab in. Druk de Swab
lichtjes tegen het onderste
gedeelte van de neus aan.

2

Breng de Swab tot in de
nasofarynx. Dit is
ongeveer de helft van de
lengte van de neus tot het
oor.

[figure not shown]
3

Draai de Swab minimaal 3
maal rond om voldoende
materiaal op te nemen

4

Verwijder de Swab uit de
neusholte.

5

Breek de Swab af in de bijhorende
tube ter hoogte van de rote lijn. Sluit
de tube en breng de patiëntgegevens
aan op de tube.

Addendum C: Poster/flyer for the recruitment

CORONAVIRUS
COVID-19

Detectie van Covid-19 in tranenfilm

Gezocht: deelnemers >18 jaar met vermoeden van COVID-19 (en getest).

Wat?
Het Covid-19 virus is mogelijk te detecteren in de tranenfilm. Bij deze studie wordt er naast een neuswissel ook een staal van het oogoppervlak afgenoem, om aan te tonen of het virus al dan niet terug te vinden is in tranen.

Wat wordt er van u verwacht?

Invullen korte vragenlijst → Wissel van het oog

Wat zijn de voordelen voor u?
U hebt geen direct voordeel aan uw deelname maar u draagt wel bij aan de evolutie van de wetenschap.

Meer informatie?
Vragen omrond dit onderzoek? Interesse om deel te nemen? Laat uw gegevens achter bij afname van de nasofaryngeale wissel of contacteer ons.
[contact]
E-mail: [contact]

Deze studie werd goedgekeurd door de Ethische Commissie Onderzoek UZ/KU Leuven onder S 64002.

Universitair Ziekenhuis Leuven

Tear film SARS-nCoV-2 detection in symptomatic and pauci-symptomatic patients.

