Presumably, the rate of pauci-symptomatic carriers is higher within health care workers compared to the general population. Emergency patients and health care workers are preferred over pauci-symptomatic pre-operative patients, since prevalence of SARS-nCoV-2 is low in these pre-operative patients (data UZ Leuven Laboratory Medicine (1 June 2020): prevalence of around 0.2%). Similar to the symptomatic patients, all volunteers will be informed about our project and asked to sign an informed consent for simultaneous swabbing of the conjunctiva and the nasopharynx. The pauci-symptomatic group will include only volunteers already listed for nasopharyngeal swabbing based on their symptoms (to avoid unnecessary use of nasopharyngeal swabs). By testing pauci-symptomatic volunteers, we intend to better substantiate current guidelines in ophthalmology practice. Mostly “deemed-healthy” patients visit outpatient clinics, but when carrying the virus, they are the highest risk of contaminating health care workers. Proving presence of (viable) SARS-nCoV-2 virus in the tear film of pauci-symptomatic volunteers might change our ophthalmology practice in the long run. Furthermore, we want to compare results of both the ocular and nasopharyngeal swab (both positive for SARS-nCoV-2; both negative for SARS-nCoV-2; discordant results, with either eye or nasopharynx positive and the corresponding sample negative for SARS-nCoV-2). For patients with discordant results, we purpose to identify potential correlations between disease-severity and detection of SARS-nCoV-2 in different body fluids by using the same questionnaire mentioned above (*cf. Addendum A*). The difference in RNA viral load (by means of quantitative result (Cycle threshold (Ct) of the SARS-CoV-2 PCR) in the tears of different patients at different moments in time (i.e. the assessment of the evolution of quantitative result) will be indicative for the transmissibility of the virus. However, to evaluate genuine transmissibility, swabs positive for SARS-CoV-2 via qPCR will be sent to the REGA institute (i.e. the Laboratory of [name]) for **viral culture and detection of subgenomic (sg) RNA**. This is in contrast to most previously published studies focusing only on the detection of SARS-CoV-2 RNA by PCR. SARS-CoV-2 PCR is not able to differentiate between live or dead virus (6–8). It is important to make that difference in order to draw conclusions on potential transmission of the virus by tears. Detection by culture indicates if viable virus is present in the sample. Detection of sgRNA is an indicator for replication of the virus. The viability of the virus collected from tear samples will determine the risk of spreading the virus via tears.

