
Emergency patients, health care workers and patients hospitalized for a different condition/reason with a limited amount of symptoms (cfr. Inclusion criteria) that apply for a nasopharyngeal swab to confirm COVID-19 will be informed about the study by a pre-indicated health care worker.

When the patient is interested in participating he/she will be informed about the study goals by the same health care worker. The volunteer will receive an information letter and a copy of the informed consent to take home.

After signing the informed consent, each patient will be asked to fill in a questionnaire (cfr. *Addendum A*).

Study procedure

The conjunctival swabbing has been explained in detail in part 1.

3. Selection and withdrawal of subjects

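### Do the two different interim storage instructions for the conjunctival swab in Addendum B call for a change to the plan?

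*Combined protocol and SAP*

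**What the plan says.** Section 2.1 (Part 1, study procedure) has each swab placed in transport medium and "transferred to a -80°C freezer until further processing". It names no interim step, and it refers to Addendum B for the training of samplers. Part 2 adopts the same procedure: "The conjunctival swabbing has been explained in detail in part 1".

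Addendum B, which is in Dutch, covers the interim step twice:

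- **Numbered steps 3 and 4.** "Plaats het UTM met staal in de koelkast op -18°C", then "Binnen de 24 u moet het UTM met staal verplaatst worden naar -80°C". That is a nominal -18°C with transfer to -80°C within 24 hours.
- **Last caption of the eyelid-swab sequence.** "bewaar deze in de diepvries bij -20°C gedurende maximaal 2 dagen, nadien te bewaren op -80°C". That is -20°C for at most two days, then -80°C.

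On later use of the samples, section 1 states that "swabs positive for SARS-CoV-2 via qPCR will be sent to the REGA institute" for culture and subgenomic RNA testing, and that "Detection by culture indicates if viable virus is present in the sample". Secondary outcome 7 in section 2 reads: "Exploring the replication of the SARS-nCoV-2 virus, by differentiating between death and alive SARS-nCoV-2 virus through sg RNA-testing and tissue culture".

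**The concern.** Two written rules for one tube look like a protocol defect, and here both sit on the page from which nurses, students and residents are trained. Two samplers could each believe they comply while holding tubes for different times. A tube moved at 36 hours obeys the caption and breaches step 4. Because Part 2 refers back to Part 1, the discrepancy covers both parts of the study.

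The stake would be the viability work. Section 1 presents culture and subgenomic RNA as what sets this study apart from earlier work that relied on PCR alone. If hold time before deep freezing affected whether virus could be grown, a PCR-positive, culture-negative swab might reflect handling and not the absence of live virus. The plan also describes no record of hold time per tube that would let a reader judge this.

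**Working it through.** No sample size, error rate or power figure is involved, and the plan gives no figure to reproduce. The check compares the instructions directly.

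**Inputs**

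| Source | Interim temperature | Limit before -80°C | Final storage |
|---|---|---|---|
| Section 2.1 | none given | none given | -80°C |
| Addendum B, steps 3 and 4 | -18°C | 24 h | -80°C |
| Addendum B, last caption | -20°C | 2 days | -80°C |

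**Step 1: do both rules concern the same swab?** Yes. The caption closes a sequence about sliding the brush along the inside of the eyelid. The nasopharyngeal procedure follows under its own heading.

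**Step 2: size of the gap.** 2 days × 24 h = 48 h. Difference in limits: 48 − 24 = 24 h. Difference in temperature: −18 − (−20) = 2°C.

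**Step 3: which tubes are affected by the time limits?** Let t be the time from collection to -80°C.

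| t | Step 4 | Caption |
|---|---|---|
| up to 24 h | met | met |
| over 24 h, up to 48 h | breached | met |
| over 48 h | breached | breached |

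The rules disagree only in the middle row. A sampler who follows the numbered steps breaches neither time limit.

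**Step 4: is section 2.1 in conflict?** No. It states the destination that both rules share and leaves the interim detail to the addendum, which is ordinary drafting.

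**Step 5: does the discrepancy create the ambiguity in a negative culture?** No. Under section 2.1 every tube is frozen until processing, so a negative culture on a PCR-positive swab could reflect storage loss under either rule alone. Nor does one rule remove variation in hold time: step 4 permits 0 to 24 h and the caption 0 to 48 h.

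**Step 6: what would reconciliation change?** If the sponsor kept the two-day limit, every hold time now allowed by either rule would stay allowed, and no handling need change. If the sponsor kept the 24 h limit, only tubes in the 24 to 48 h window would be treated differently. The documents give neither their number nor any stability data at these temperatures. Section 7.2 names no test for the culture or subgenomic RNA results, so no planned p-value or interval for that outcome depends on the choice.

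**The case for a change.** The best case for a change is that the contradiction is plain in the text, is not an artefact of extraction, and costs little to remove. Both instructions are complete sentences. One caption also cross-refers to point 4 for rotating the brush, while rotation is item 1 in the list. That is a weak sign that the two blocks were never aligned, although lost figure numbering could explain it too. A sample used to judge viability ought to have one traceable handling rule, and two time entries per tube would be a small burden.

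Most of the textual part stands: there are two instructions, they differ, and nothing ranks them. The consequence does not stand. Extra variation in hold time arises only if some samplers use the caption's second day, and no document says that they do. Nothing in the documents links 24 h against 48 h, or a 2°C difference, to any result, whether PCR, Ct value, culture or subgenomic RNA.

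The request for a per-tube time record is a separate matter. It would be just as useful, or as dispensable, under a single rule. Section 12 names the study database without listing its variables, so such a record may already exist.

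**Conclusion.** No change to the plan follows. Addendum B contains a clerical discrepancy: two interim storage instructions, 24 h and 2°C apart, that lead to the same -80°C storage and can both be met on time by moving the tube within 24 h. As far as the documents show, results obtained under either instruction are equally sound, and the outcome most often linked to viability is worded as exploratory in a study that calls itself exploratory.

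This rests on two points. First, the documents contain no stability data and do not say how many tubes were held for 24 to 48 h, so an effect is neither shown nor excluded; its size is unknown. Second, both storage sentences are taken as extracted, although the order and numbering of that page may differ from the original. Harmonising the wording of Addendum B when the page is next revised would be good housekeeping, with the choice left to the sponsor. It would not alter the design, the analysis or any conclusion that the documents let us assess.
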